5. An informant	5. Inner ear disease
	6. Claustrophobia
	7. Cholinesterase inhibitors
	8. Subjects with an indication for HBOT
	9. Individuals with previous HBOT treatments.
	10. Individuals with cancer and other medical illnesses requiring intensive therapy.
	11. Individuals with proliferative retinopathy.

since the HBOT treatment will be performed in Asaf Harofeh, located in central Israel. The treatment is very time consuming and far away participants may have a hard time complying to the treatment protocol.

D2b. Recruitment- Subjects will be recruited through talks in the community, advertisements, and companies which have large lists of elderly interested in receiving emails about health related topics. IDCD subjects diagnosed at follow up with MCI (21% at the 36-months follow up) will be offered participation in the proposed trial. Although the IDCD study participation was far less demanding than the proposed RCT, recruiting 1200 subjects within 2 years reinforces our confidence in recruiting 154 subjects for this RCT—including many already in the IDCD—in 3 1/2 years. Additional recruitment will be performed through clinics (e.g. diabetes and executive clinics).

Table 2- Summary of study procedures

	Screen	Baseline/ beginning of intervention	12 weeks /end of intervention	6 months	12 months
Informed consent	X				
History, cognitive assessment (for MCI classification), clinical evaluation	X				
Medication review	X	X	X	X	X
Physical exam	X		X		
Blood test		X	X		X
Follow up information		X	X	X	X
Adverse event monitoring*			X*		
Group assignment: review program and expectations at time of randomization		X			
Cognitive testing (ADAS COG13+executive functions tests)		X	X	X	X
Functional assessment (CDR)	X		X	X	X
ADL, IADL		X	X	X	X
Depression questionnaire	X		X	X	X
MRI ASL		X	X		X
FDG-PET		X	X		X
Blindness testing			X		
The intervention will begin within three weeks after the Baseline assessments and end at 12 weeks after 60 HBOT/Sham treatments. A physician is always present during the HBOT sessions, and a nurse is in the chamber throughout the whole treatment, so adverse events will be de facto closely monitored at each session up to the end of the intervention.					

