D2c. Procedures- **Table 2** presents study procedures for each subject. HBOT sessions will take place in Asaf Harofeh Medical Center; informed consent and all other assessments, including cognitive, functional, MRI, and FDG-PET will be performed at the Sheba Medical Center. Adverse event monitoring is done at every HBOT and sham session, by a nurse in the chamber throughout the session and a physician always present. Physical exams and blood collection for safety monitoring will occur before randomization, and at 12 weeks. Medication review will occur before randomization, before and after the intervention, and 6 and 12 months later, with cognitive testing at these times except before randomization. The T2D-related biomarkers (Blood test, MRI ASL and FDG-PET) will be assessed before and after the intervention, and 12 months later. After intervention, a questionnaire will examine whether blindness was maintained. At the end of the participant's 12 months' participation in the trial, the participant can choose to receive HBOT treatment for which the costs will be covered by the study team. At the end of the second HBOT treatment course, an additional neuropsychological assessment will be administered to the participants.

D2d. Randomization and Blinding of Intervention-Eligible candidates will be randomized with equal probability to the HBOT and sham interventions. When a cluster of at least 3 subjects from one of the interventions is filled, the intervention for that cluster will begin (77 subjects will be recruited for each treatment). Clusters will be a random effect in the analyses (see D6). Three study technicians who activate HBOT or sham protocol sessions will be the only unblinded staff who have the key for the subjects' group assignments. All subjects and other clinic staff will remain blinded to group assignment. Study nurses will monitor AEs during all sessions and a physician will be present during each session. Importantly, staff from Sheba, who assesses outcomes, will not be exposed to the subjects during their intervention and vice-versa.

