b. Protection Against Risk. The overall risks of this proposal are small. Potential risks will be minimized by enrolling only participants who meet eligibility requirements and have undergone screening medical assessment, including laboratory tests, to ensure health status, warning subjects and their caregivers of potential study risks, inquiring about potential adverse reactions at regular intervals and performing screening laboratory tests at regular intervals to help ensure continuing good health. Professional treatment will not be altered or modified for research purposes. Subjects are informed that they may terminate testing at any time should they find any aspect objectionable. The interviewers and research assistants will be clinically trained and sensitive to signs of stress, anxiety and/or fatigue. In the event that study participation results in injury or illness requiring emergency medical treatment, appropriate acute medical care will be provided at no cost to the subject. A Data Safety and Monitoring Board will be established to monitor adverse events and other safety concerns.

Protection of **patient confidentiality** and privacy will be rigorously guarded through several measures: 1) by the assignment of coded numbers to each file in the computer database; 2) storage of written information in locked filing cabinets at all times; 3) storage of electronic information in databases accessible only through a password that is not available to anyone outside of the study staff; and 4) no use of names or other identifying information in publications or other publicly available documents. However, subjects will be told that should confidential information be accidentally disclosed to the wrong party, it could have adverse consequences for the subject in terms of liability in legal proceedings, or discrimination in obtaining life or private health insurance. Again, we note that Israelis have the right for complete health coverage.

3. Potential Benefits of the Proposed Research to the Subjects and Others

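### No adverse event inquiry is scheduled outside the chamber sessions, so subjects who stop sessions and everyone at the 6- and 12-month visits are not asked in any defined way

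*Combined protocol and SAP*

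**What the plan says.** Table 2 in section D2b has a row headed "Adverse event monitoring" with a single mark, under 12 weeks/end of intervention. The note below the table explains that staff are present at each session, "so adverse events will be de facto closely monitored at each session up to the end of the intervention". D2c gives the procedure: "Adverse event monitoring is done at every HBOT and sham session, by a nurse in the chamber throughout the session and a physician always present". D2d has the study nurses monitor events during sessions, and D2e has a nurse ask about changes in medical condition when subjects arrive for a session.

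Other safety-relevant items sit outside the sessions. D2c states: "Physical exams and blood collection for safety monitoring will occur before randomization, and at 12 weeks". It also states: "Medication review will occur before randomization, before and after the intervention, and 6 and 12 months later". Table 2 adds a row called *Follow up information* at baseline, 12 weeks, 6 months and 12 months, and its content is not defined. A 12-month blood test is also planned, but D2c classes it with the diabetes-related biomarkers.

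Two later sections are broader. E.2.b (Protection Against Risk) lists, among its protections, "inquiring about potential adverse reactions at regular intervals". E.6.b (Safety Monitoring) has events monitored in real time, recorded on a specific form and followed until they resolve. Serious events go to the IRBs within 24 hours of the team learning of them, and to the DSMB within 48 hours. E.6.b gives no start or end to the collection period.

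For subjects who withdraw from the intervention, D2g promises an attempt to assess outcomes and does not mention adverse events. D6 keeps them in the intent-to-treat population. After 12 months, D2c says "the participant can choose to receive HBOT treatment for which the costs will be covered by the study team". The only assessment it names for that course is neuropsychological.

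**The concern.** If adverse events are sought only at sessions, ascertainment depends on attendance. A subject who stops because of an adverse event leaves the monitoring at the moment when it would be most informative, yet stays in the efficacy analysis. The pitfalls section (D2J) expects that dropout may be higher in the sham arm, so the loss of safety information could differ by arm. D2i reads a between-arm withdrawal difference above 15% as a sign of perceived treatment or lack of confidence. Without asking those who stopped, withdrawal caused by adverse events is harder to separate from that explanation.

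The later visits matter for a second reason. E.2.a describes reversible myopia and pulmonary oxygen toxicity as possible effects. Whether such effects have resolved, in someone who no longer attends sessions, can be learned only by asking later. The plan describes HBOT as relatively safe (C1) and well tolerated (D8), and the pilot is meant to inform a large multi-center trial. Its safety record is therefore one of its products.

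**Working it through.** The plan states no figure on this point, so there is none to reproduce. The check sets the sections side by side and then does one piece of arithmetic on time covered.

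**Where an adverse event question is scheduled**

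| Situation | Defined adverse event inquiry | Other items scheduled |
|---|---|---|
| Attending sessions | Yes: every session (Table 2 note, D2c, D2d, D2e) | – |
| 12-week visit, sessions completed | Only through the sessions up to that point | Physical exam, safety bloods, medication review, *Follow up information* |
| 12-week visit, sessions stopped early | None after the last session attended | Same items; D2g promises only an attempt to assess outcomes |
| 6 months | None | Medication review, *Follow up information* |
| 12 months | None | Medication review, *Follow up information*, biomarker blood test |
| Optional HBOT course | Not stated; D2c's wording on every HBOT session could cover it | Neuropsychological assessment at the end |

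**Do E.2.b and E.6.b fill the empty cells?** E.2.b promises periodic inquiry but names no visit, and Table 2 shows no such inquiry away from the sessions. E.6.b governs what happens once an event is known: recording, grading, follow-up to resolution and SAE reporting. Its SAE clock starts when the team learns of the event. Neither section schedules a question.

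**Who would ask?** Under D2c, sessions take place at Asaf Harofeh and all other assessments at Sheba. The adverse event duty is given to the session staff. No section gives the staff at the Sheba visits an adverse event question.

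**Time covered**

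- Treatment period: 60 sessions / 5 per week = 12 weeks (D2e), which agrees with Table 2.
- Total follow-up: 52 weeks if the 12-month visit is counted from baseline. It is 12 + 52 = 64 weeks if counted from the end of treatment, as the opening aims and D2j describe it.
- Share of time with scheduled inquiry = 12 / total weeks: 12/52 = 23%; 12/64 = 19%.
- Share without it: 77% to 81%.

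This is a share of calendar time. It does not estimate the share of events missed, because risk is not uniform over the period.

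**The case against.** The best reply is that the plan is not silent on safety beyond the sessions, and much of that stands.

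- A reader might infer that adverse events are collected only at sessions. The documents do not support that: E.6.b requires all events to be recorded, with no end date, and E.2.b promises inquiry at intervals.
- A reader might also infer that no safety data are scheduled once sessions stop. That is wrong too. The 12-week exam and safety bloods belong to a visit and not to a session, and medication review and *Follow up information* continue to 12 months. The latter might include an adverse event question, but its content is not defined.
- The optional course may already be covered by D2c's wording. It also follows the 12 months of trial participation, so it cannot distort the randomised comparison. The text is silent there and shows no exclusion.
- Benefit and risk are not assessed over unequal windows in the primary analysis. D6 takes the primary comparison from baseline to 12 weeks, which matches the session window; the 6- and 12-month analyses are secondary or exploratory.
- It is tempting to apply the 13% dropout allowance in D7 to 154 subjects (0.13 × 154 = 20) and say that about 20 would have truncated safety follow-up. D7 uses the 13% to inflate 67 per arm to 77. It does not count subjects who stop sessions but stay in follow-up, so the plan gives no such number.
- The risks listed in E.2.a are mainly tied to exposure, no late-onset harm is identified, and events that are already known must be followed to resolution.

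What remains is that none of these provisions is a defined adverse event query at a named visit. An event that nobody asks about may never reach the reporting steps in E.6.b.

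**Conclusion.** The concern holds as a gap in scheduled inquiry and an unreconciled difference between sections. Followed as written, Table 2 and D2c ask no adverse event question of subjects after they stop sessions, nor of anyone at 6 or 12 months. E.2.b and E.6.b imply broader collection without scheduling it. Scheduled inquiry covers 19% to 23% of follow-up time, depending on how the 12-month visit is counted.

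This rests on two readings: that *Follow up information*, being undefined, cannot be credited as an adverse event query, and that E.2.b's intervals are not specified elsewhere in the document. If an operations manual defines either one, the remedy is to bring that definition into the protocol. The number of events at risk of being missed cannot be derived from the plan. The primary efficacy analysis is unaffected.

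**What to change.** Reconcile Table 2 and D2c with E.2.b and E.6.b, and state when adverse event collection starts and ends.

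- Add a standard AE/SAE query, including resolution of earlier events, at the existing 12-week visit for all randomised subjects, including those who stopped sessions.
- Add the same query at the existing 6- and 12-month visits.
- Define what *Follow up information* contains.
- In D6, which describes efficacy analyses and no adverse event tabulation, add a report of events by randomised arm for the treatment period and for full follow-up.
- State that session-based monitoring also applies to the optional HBOT course, and report those events separately.

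The cost is a few minutes at visits that already take place, plus the added safety tables. More unrelated events will be recorded in an elderly population; reporting by arm helps put these in context. Subjects who leave the study entirely will not attend these visits, so the query will not recover their events.

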The team members present at all times during the HBOT/sham sessions are a physician, two nurses (one inside the chamber and one outside), and at least one of the three unblinded technicians. Only study subjects—not clinical patients—are in the chamber during research hours. When subjects arrive at the Hyperbaric Unit, one of the nurses signs them in; measures their glucose, blood pressure, heart beat, and temperature; and asks about any change in their medical condition. Subjects with signs of any infectious disease (such as upper respiratory tract infection), or arriving with systolic blood pressure >170mmHg or <90mmHg, or glucose <75mg/dl do not enter until it improves. While in the chamber, subjects may drink, read, write, sleep, hear music with headphones, or watch TV. Video games, laptops, phones, or other electronic devices are not allowed in the chamber. Subjects have their own masks. The atmospheric pressure goes up to 2.0 ATA during the first five minutes of the session, with a noise of circulating air. Subjects will feel pressure in their ears; the nurse will advise releasing the pressure by pumping the ears (closing their nose with their fingers and pushing air). In the last five minutes of the session, the pressure is slowly decreased to 1ATA.

D2f. Sham intervention- Sham was selected as the control condition rather than “usual care” to equate intervention groups with respect to other variables that could influence cognition and functional status, such as a new challenge (completing an activity program), peer socialization, and attention from staff.

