Except for pressure, all the conditions of the HBOT intervention are provided in the sham intervention (nurse measures vitals and asks about health before entering the chamber, time in the chamber, number of sessions per week and overall, nurse in the chamber at all times, mask on the face, etc.). In contrast to 2 ATA for the HBOT, the sham condition pressure goes up to 1.1 ATA during the five first minutes of the session with noise of circulating air. This provides a minimal pressure sensation in the ears, with the same nurse advice on pumping the ears. Pressure then decreases very slowly during the next half hour; in the last 5 minutes of the session, the air is circulated again with its related noise. Sham and HBOT sessions will never be adjacent, so subjects from the two groups cannot meet and compare sessions. This sham model makes the two conditions very comparable, except for the hyperbaric effect, to minimize breaking the subjects’ blindness.

Consideration of alternative sham and HBOT conditions: The two clinical trials described in the preliminary data section had a treatment group and a crossover group (assessed at baseline, after two months with no intervention, and again after HBOT intervention). A more effective design is a sham condition that is very similar to the HBOT condition but without known treatment effects (and also permitting the assessment of the long-term effect of HBOT). We considered a sham condition using a slightly higher 1.3 ATA level, but this hyperbaric condition has an increase in tissue oxygenation greater than 50%⁹², which may have substantial physiological effects, so 1.1 ATA for sham is preferable. We considered 100% oxygen with 2.5 ATA in the HBOT condition, but in our experience, this protocol induced more adverse events.

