D2J. Pitfalls and solutions- Potentially larger sham dropout rates- The sham group will feel less ear pressure than the HBOT group. Since the intervention is time consuming, there may be more dropouts among those who think they are in the control group. In the majority of RCTs of behavioral interventions, there are no differences in the dropout rates of control groups^{e.g.113-117}. All subjects will be told that they will be randomized to high or low hyperbaric pressure, and that it is unknown yet if either works. At the end of the participant's 12 months participation in the trial, the participant can choose to receive HBOT treatment for which the costs will be covered by the study team. At the end of the second HBOT treatment course, an additional neuropsychological assessment will be administered to participants. The nurse might perceive the difference between HBOT and sham but will be instructed not to discuss this with participants. No non-T2D control arms- inclusion of non-T2D parallel HBOT and sham arms would show whether efficacy is specific to T2D, or generalizes to all MCI patients. However, for this pilot funding mechanism, the aim is proof of concept that HBOT improves cognition, focusing on T2D-MCI patients, who are enriched in cerebrovascular disease—the main target of HBOT—and at high risk for decline, improving statistical power. With ½ of the US elderly suffering from T2D or pre-T2D, this study has potential for broad public health impact. Collecting AD neuropathology data- *Despite associations of insulin with amyloid¹¹⁸⁻¹²⁰ and of T2D with tau pathology¹²¹, we decided against measuring them in CSF, due to a focus on vascular mechanisms, incomplete scientific evidence supporting AD neuropathology as an HBOT mechanistic target in a T2D context, and minimizing participants' burden.*

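### The plan says all clinic staff except three technicians stay blinded, yet it concedes that the in-chamber nurse, who monitors adverse events and coaches subjects, might perceive the arm

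*Combined protocol and SAP*

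**What the plan says.** On who is unblinded, D2d states: "Three study technicians who activate HBOT or sham protocol sessions will be the only unblinded staff who have the key for the subjects' group assignments". It then extends blinding to everyone else and gives the nurses the monitoring role: "All subjects and other clinic staff will remain blinded to group assignment. Study nurses will monitor AEs during all sessions".

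On where the monitor sits, D2c states: "Adverse event monitoring is done at every HBOT and sham session, by a nurse in the chamber throughout the session and a physician always present". D2e lists those present at each session as "a physician, two nurses (one inside the chamber and one outside), and at least one of the three unblinded technicians". It leaves sign-in, including the question about changes in medical condition, to either nurse.

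On what the inside nurse is exposed to, D2e says of HBOT: "The atmospheric pressure goes up to 2.0 ATA during the first five minutes of the session, with a noise of circulating air". D2f says of sham: "the sham condition pressure goes up to 1.1 ATA during the five first minutes of the session with noise of circulating air", followed by "Pressure then decreases very slowly during the next half hour". In both arms the nurse advises subjects on clearing their ears.

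On whether the nurse can tell, D2J (Pitfalls and solutions) states: "The nurse might perceive the difference between HBOT and sham but will be instructed not to discuss this with participants".

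D2i plans a blinding check through participants' guesses, a questionnaire and a comparison of withdrawal rates. Section E.6.b gives severity and attribution of adverse events to a group of investigators, two of them physicians, with the project director, coordinators and IRBs. It does not say whether that group is masked.

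**The concern.** D2d and D2J describe the same nurse in incompatible terms. One section places the nurse among staff who remain blinded; the other accepts that the nurse may notice which intervention is running. The only safeguard concerns what the nurse says to participants. It does not touch which complaints the nurse asks about, which are written down, or how they are first described to those who grade them.

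Two things are at stake. The first is ascertainment of adverse events, above all subjective ear and sinus complaints, which depend on being asked about. The second is the purpose of the sham. D2f chose it over usual care partly to equalise staff attention, and D2J worries about dropout among subjects who believe they are controls. A nurse who has inferred the arm could affect expectation or encouragement without discussing the arm at all.

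**Working it through.** The plan gives no figure for staff blinding, so there is none to reproduce. The check is a comparison of sections with some simple arithmetic.

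**1. Do the statements conflict?** The D2d sentence on technicians could be read narrowly, as being about who holds the allocation key. The next sentence removes that reading, because it claims blinding for all other clinic staff. D2J's concession cannot stand beside it unqualified.

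**2. How different are the sessions for someone inside?** Inputs: peak 2.0 ATA (D2e), peak 1.1 ATA (D2f), ambient 1 ATA.
- HBOT rise above ambient: 2.0 − 1.0 = 1.0 atm.
- Sham rise above ambient: 1.1 − 1.0 = 0.1 atm.
- Ratio: 1.0 / 0.1 = 10.

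The sham peak is not held. D2f has pressure falling over the half hour after the first five minutes, with air noise only at the end. Section E.1 instead describes 1.1 ATA in the first and last five minutes. These two accounts of sham must be reconciled, but under either the contrast at peak is tenfold.

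**3. Does recognising one session reveal more than one subject's arm?** Yes. Treatment starts in clusters of at least 3 subjects from one intervention (D2d), and a session runs at one pressure. Recognising the session identifies everyone in it. Section E.2.a says the inside nurse belongs to the Hyperbaric Unit team, so inference is plausible.

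**4. What does the nurse do that arm knowledge could affect?**

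| Step | Who, according to the plan | Masking described |
|---|---|---|
| Sign-in health questions (D2e) | either nurse | general claim in D2d only |
| In-session monitoring (D2c, D2d) | inside nurse, physician present | general claim, qualified by D2J |
| Ear-clearing advice (D2e, D2f) | nurse, same advice in both arms | no script specified |
| Severity and attribution (E.6.b) | wider safety group | not stated |
| Cognitive, functional, imaging outcomes (D2c, D2d) | Sheba staff, not exposed to subjects during treatment | separated |
| Check of blinding (D2i) | participants only | nurses not asked |

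**5. How many events might be involved?** Section E.2.a puts middle-ear barotrauma below 2%, without a denominator in that sentence. I assume per patient, because the next sentence uses patients as its base.
- Per patient: 77 × 0.02 = 1.54, so at most about 1.5 events in the HBOT arm.
- If it meant per session: 77 × 60 × 0.02 = 92.4, so at most about 92.

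Both are ceilings. Neither measures bias: the documents give no basis for the number of events that might be elicited or recorded differently.

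**The case against.** The strongest reply is that the plan discloses this weakness itself, with a mitigation, and has other protections. That is largely fair. Sheba assessors do not meet subjects during treatment. Subjects are told that they will receive high or low pressure and that it is unknown whether either works. Sham includes the same pre-entry checks and ear advice. Severity and attribution do not rest with the chamber nurse. The DSMB initially sees data blinded to treatment. D2i's guess question and withdrawal comparison bear on the expectancy route.

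Several stronger readings are tempting, and the documents do not support them:
- A reader might infer that the nurse knows the arm. D2J says only that the nurse might perceive it, and only technicians hold the key. Probable inference is as far as the text goes.
- A reader might picture one nurse accompanying a subject for all 60 × 1.5 = 90 hours of sessions. The plan gives roles, not rosters.
- A reader might infer that an adverse-event comparison will be presented as blinded. D6 specifies no between-arm adverse-event analysis, and no section promises such a description.
- A reader might infer that a few misrecorded events would multiply the safety contrast. That needs an invented count set against a ceiling with an unstated denominator.

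What remains after these concessions is the conflict between D2d and D2J and the lack of any described step that keeps elicitation, first reporting or grading masked. Disclosure in one section does not correct the opposite statement in another.

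**Conclusion.** The point holds in a limited form. D2d claims blinding of all clinic staff other than the technicians, which the design does not reliably deliver for the inside nurse, and D2J says as much. The exposure is mainly in eliciting and first reporting adverse events during sessions. An effect on efficacy is possible only indirectly, through expectancy, encouragement or dropout. A reader should not conclude that the primary cognitive outcome is rated by unblinded staff, since the Sheba separation guards against that.

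The size of any ascertainment bias is unknown. Expected middle-ear events in the HBOT arm are at most about 1.5, assuming the cited incidence is per patient. The conclusion also assumes that a tenfold difference in peak pressure rise is often noticeable to unit staff in the chamber. That is plausible and consistent with D2J, but not demonstrated. This should be corrected; it does not undermine the trial's primary comparison.

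**What to change.** 1. In D2d, reconcile the blinding sentences with D2J: state that inside-chamber nurses may infer the arm, and describe in-session adverse-event collection as potentially unblinded.
2. Where staffing allows, have the outside nurse already present, rather than either nurse, ask the sign-in questions, using one fixed symptom checklist in both arms. Script the ear-clearing advice. This reduces the problem but does not guarantee masking, because the outside nurse works alongside an unblinded technician.
3. In E.6.b, have severity and attribution of non-urgent events assigned from written reports with arm, pressure and cluster removed.
4. Optionally, add the nurses' guess of arm to the D2i blinding check.

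The cost is protocol wording, a checklist, a short script, less flexible nurse rostering and some redaction work. It uses staff already listed in D2e. In-session safety monitoring and emergency roles are left as the plan has them.
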